1.2.3 Implications for the study

There is insufficient information about any of the surgical options to guide management of any type of pelvic organ prolapse in any population of women with prolapse. We have identified that the largest group of women are those with anterior and/or posterior prolapse, who comprise around 90% of those having prolapse surgery (including those having a concomitant hysterectomy). The evidence base for treating these women is clearly inadequate, with very little evidence regarding subjective prolapse symptoms, effect on quality of life and safety. In particular, the routine use in the NHS of mesh for prolapse surgery should be informed by well designed RCTs.

The current application will fulfil the research need identified by the Cochrane Review¹ and the IP review⁴ for adequately powered RCTs of the use of mesh in prolapse surgery. It will comprise the largest, only adequately powered and independent RCT comparing traditional prolapse operations with new methods incorporating mesh as an inlay or mesh inserted using an introducer system. We will take account of the different clinical characteristics of women having primary as opposed to secondary surgery, and identify confounding factors which may predict outcomes.

1.3 The operations

This trial is concerned with surgical operations for vaginal wall pelvic organ prolapse:

- anterior vaginal wall prolapse (urethrocele, cystocele, paravaginal defect);
- posterior vaginal wall prolapse (enterocele, rectocele, perineal deficiency).

A woman may present with prolapse of one or both of these sites, and she may be having a primary or a secondary procedure. For each of these sites there are several alternative traditional surgical techniques, none of which have been properly evaluated in adequately powered multicentre RCTs. The techniques for performing anterior or posterior repair or implanting mesh or graft can vary widely between gynaecologists. These include:

a) Standard anterior and/or posterior repair

In the standard approach, the vaginal skin is opened in the midline, the fascia is separated from the skin and the fascial defect is plicated (sutured or buttressed), usually in the midline. Any redundant vaginal skin is excised and the skin is closed.

b) Standard repair with mesh inlay

Over the last 10 years, gynaecologists have begun to include small pieces of mesh inlays as an extra support to the fascial defects through which the pelvic organs prolapse, analogous to the use of mesh in hernia surgery.²⁷ If mesh is used, it can be positioned over or under the fascial defect as a 'mesh inlay' and sutured in place to reinforce the tissues.

The proposed advantage of using mesh is that it will optimise surgical outcome without compromising vaginal capacity or sexual function.²⁸ The rationale is that it

may help to reduce failure rates from breakdown of weakened tissue or failure to identify all fascial defects. Although the mesh materials used may be stronger than the woman's own fascial tissue, the indications for use and choice of materials remain controversial. The extent to which mesh inlays are currently used is unknown, but recent surveys suggest that many gynaecologists are already incorporating mesh into their practice both in the UK³⁰ and in America. The decision to use mesh is complicated by the different types available:

- absorbable synthetic (e.g. polyglactin);
- absorbable biological (e.g. fascia lata, porcine dermis);
- combined (e.g. polyglactin and polypropylene); and
- non-absorbable (e.g. polypropylene).

There are theoretical pros and cons to each, but there is not enough evidence available to allow rigorous comparison. Major potential adverse effects include infection, bleeding, erosion and dyspareunia as well as failure of repair and failure to cure symptoms.

c) Mesh insertion using an introducer device or kit

Most recently, some commercial manufacturers of mesh have introduced large mesh systems, analogous to, but much bigger than, the TVT slings used in incontinence surgery.³² These commercial devices or kits are available for the anterior or posterior compartments, or can be used together for both. The mesh is inserted using introducer devices. They involve blind penetration of pelvic spaces by trocars in order to thread mesh tails into positions from which they support a central mesh layer which corrects the prolapse defect. Currently available devices use non-absorbable synthetic mesh but kits using other types of mesh (combined) are being introduced.

These are being actively promoted and introduced to clinical practice without first being evaluated in rigorous independently-managed RCTs. These meshes are inserted blindly using introducer devices or trocars which may damage surrounding organs or blood vessels. Various systems are available for anterior, posterior or combined defects. Prospective studies have suggested that the mesh devices have been used in at least 500 women worldwide, but it is not clear whether this is driven by gynaecological preference or commercial marketing pressure. However, clearly some women have been willing to undergo this new technology despite lack of evidence for safety or efficacy. Information from one manufacturer suggests that they anticipate a rapidly increasing penetration of the market: while they sold 1,574 systems in 2002, they predict selling 6,367 in 2007 and 10,100 by 2010.

[figure not shown]
There is no evidence to suggest whether or not the use of mesh (particularly non-absorbable synthetic mesh which has the strongest mechanical strength and remains in situ indefinitely) should be reserved for more complex or recurrent prolapse. Although gynaecologists have stated that this is their belief and practice, ³⁰ evidence suggests that the majority (70%) of the current recipients of mesh are having their first prolapse operation. ⁴ An Interventional Procedures review with 503 women ⁴ and a further recent case series of 289²⁶ women drew attention to the high incidence of serious adverse effects (e.g. 2.8% with damage to surrounding organs) in women having mesh inserted with blind introducer devices. Our opinion is that until their benefits and risks have been properly evaluated, mesh kits using non-absorbable synthetic mesh should be reserved for more complex cases of prolapse. Therefore we will limit this option to women being treated for a recurrence of prolapse in the same site after primary surgery.

The initial purchase cost of mesh inlays (around £200 per woman) and mesh kits (around £400-600) is likely to have a significant impact on the cost of prolapse surgery. The proposed trial will provide evidence to indicate whether the extra costs of mesh are justified in terms of better outcomes for women and for the NHS.

1.4 The gynaecologists

For a gynaecologist to join the PROSPECT study, he or she must be uncertain regarding the best operative technique for repairing prolapse, and hence be willing to randomise the majority of patients. All the gynaecologists must be able to perform standard and mesh inlay repairs. Gynaecologists who are not trained (beyond the learning curve) in the use of the mesh introducer kits will only be able to randomise women to the other options.

Flow diagram
PROSPECT: PROIapse Surgery Pragmatic Evaluation and randomised Controlled Trials

PTO for explanatory notes

^{*} Only gynaecologists trained in the use of

Explanatory Notes for Flow Chart

1. Definitions of primary and secondary repairs:

Randomisation for women who had a previous repair will be based on the site of the previous surgery.

- A primary procedure is defined as the first prolapse repair in that compartment.
- A secondary procedure is defined as a repeat repair of a prolapse previously repaired in that compartment.
- If the woman has had a previous prolapse repair but she only needs a repair of a
 prolapse in a different compartment (de novo prolapse) she will be randomised as
 having primary surgery for that compartment.
- If a woman had a new (de novo) prolapse and a previously repaired prolapse
 which also needs a second repair, she will be randomised as having secondary
 surgery for that compartment. The de novo prolapse will be treated as a concomitant
 procedure (i.e. not subject to randomisation, the gynaecologist can choose the
 most appropriate prolapse procedure).

2. Concomitant procedures

All the following concomitant procedures will be allowed but must be recorded and described:

- · Continence procedure
- · Hysterectomy (vaginal or abdominal) including method of vault support
- · Vault repair
- · Sacrospinous suspension

3. Definition of trials and cohorts

Women having Primary Surgery RCT1

Stratum A: RCT in women having Primary surgery for Anterior and/or Posterior vaginal wall prolapse and surgeon able to randomise between all three arms

Stratum B: RCT in women having Primary surgery for Anterior and/or Posterior vaginal wall prolapse and surgeon able to randomise between the first two arms

Stratum C: RCT in women having Primary surgery for Anterior and/or Posterior vaginal wall prolapse and surgeon able to randomise between the first and third arm

CC1: Non-randomised Comprehensive Cohort 1 women who were eligible (having Primary surgery for Anterior or Posterior vaginal wall prolapse) but not randomised.

Women having Secondary Surgery

RCT2: RCT in women having Secondary surgery for Anterior and/or Posterior vaginal wall prolapse and surgeon able to randomise between the first two arms only and

RCT3: RCT in women having Secondary surgery for Anterior and/or Posterior vaginal wall prolapse and surgeon able to randomise between all three arms and

CC2: Non-randomised Comprehensive Cohort 2 women who were eligible (having Secondary surgery for Anterior or Posterior vaginal wall prolapse) but not randomised.

Women having other prolapse surgery

CC3: Comprehensive Cohort 3, women having other prolapse surgery only (not Anterior or Posterior vaginal wall prolapse).

V3: 01 June 2010

APPENDIX III POP-Q GRID

POP-Q RECORDING (Example of normal values)

Cervix present?	Yes 🗹	genital hiatus	perineal body	total vaginal length			
	No	3 cm	3 cm	10 cm			

External							Н	Hymen			Internal										
cm	+10	+9	+8	+7	+6	+5	+4	+3	+2	+1	0	-1	-2	-3	-4	-5	-6	-7	-8	-9	-10
.Aa														_ X _	///					///	
Ва														Х	777	1	44	44			
С																			X		/
D																					\nearrow X
Вр														Х		14	77	111			
Ap														X							
	Stage 3 or 4 (depending on TVL)							S	Stage 2 S1 Stage 0 or 1 (depending on TVL)					/L)							

POP-Q MEASUREMENTS:

The 9 measurements described below make up the POP-Q. All measurements are in centimetres. Record all measurements to the nearest 1cm using the disposable rulers provided.

The first 3 measurements are recorded in the boxes. All values are positive.

gh (genital hiatus) is measured from the middle of the external

urethral meatus to the posterior midline

hymen.

pb (perineal body) is measured from the posterior margin of the

genital hiatus to the midanal opening.

tvl (total vaginal length) is the greatest depth when point C or D is

reduced to its normal position.

Aa Ba C Bp Ap Bp Ap Bp Ap

The remaining 6 measurements are vaginal points which can be negative (internal) or positive (external). Record each point on the grid by marking a cross in the centre of the corresponding box.

Points on the anterior vaginal wall:

- Aa is located in the midline of the anterior vaginal wall 3cm proximal to the external urethral meatus (range -3 to +3cm).
- **Ba** is a point that represents the most distal (most dependent) position of any part of the upper anterior vaginal wall from the vaginal cuff/anterior fornix to point Aa.

Points on the upper vagina:

- is a point that represents either the most distal (most dependent) edge of the cervix or the leading edge of the vaginal cuff (hysterectomy scar/vault).
- **D** is a point that represents the location of the posterior fornix (or pouch of Douglas) in a woman who still has a cervix. Point D is omitted in the absence of the cervix.

Points on the posterior vaginal wall:

- Ap is located in the midline of the posterior vaginal wall 3cm proximal to the hymen (range -3 to +3cm).
- **Bp** is a point that represents the most distal (most dependent) position of any part of the upper posterior vaginal wall from the posterior vaginal fornix (D) or vaginal cuff (C) to point Ap.

All 9 values must be filled in, except D if the woman has had a total hysterectomy: then record vault = C.

[figure not shown]
EXAMINATION CONDITIONS:

- 1. Ideally bladder should be emptied by spontaneous void prior to examination.
- 2. Woman positioned supine on examination couch with head rest raised to 45°.
- 3. Record content of rectum and bladder.
- 4. Ensure maximum protrusion of prolapse is seen (all measurements except total vaginal length are taken while patient is bearing down).
- 5. Use vaginal speculum to examine vaginal walls separately.

STAGING THE PROLAPSE:

Stages are assigned according to the most severe portion of the prolapse when the full extent of the protrusion has been demonstrated.

Stage 0	No prolapse is demonstrated. Points Aa, Ap, Ba and Bp are all at -3cm and point C or D is between –tvl and –(tvl-2) cms.
Stage I	The criteria for stage 0 are not met, but the most distal portion of the prolapse is >1cm above the level of the hymen.
Stage II	The most distal portion of the prolapse is ≤ 1 cm proximal (above) to or distal (below) to the plane of the hymen (≥ -1 cm but $\leq +1$ cm)
Stage III	The most distal portion of the prolapse is >1cm below the plane of the hymen but protrudes no further than 2cm less than the tvl in cm.
Stage IV	Essentially, complete eversion of the total length of the lower genital tract is demonstrated. The distal portion of the prolapse protrudes to at least tvl-2cm. In most instances, the leading edge of stage IV prolapse will be the cervix or vaginal cuff scar.

BLUE reference measurements apply for all points RED for points Aa, Ba, Ap, Bp only GREEN for points C and D only

APPENDIX IV LONG TERM FOLLOW-UP

Background

PROSPECT (PROlapse Surgery, Pragmatic Evaluation by randomised Controlled Trial) is the largest randomised controlled trial conducted to date of the use of mesh in women having prolapse surgery. It addresses the use of no mesh, a biological mesh inlay, and a nonabsorbable mesh inserted as an inlay or used in a kit; and separately in women having their first prolapse operation or repeat surgery.

PROSPECT recruited 3091 women from 35 centres across the UK between January 2010 and August 2013. There were two trials, one amongst women having their first prolapse operation (Primary trial, where 1353 women were randomised to no mesh, non-absorbable mesh inlay or biological mesh inlay); and those having repeat surgery (Secondary trial, where 155 women were randomised to no mesh, non-absorbable mesh inlay or mesh kit). Women who were not eligible for randomisation were enrolled into the Comprehensive Cohort (1583 women). The following information was collected:

- Demographic and surgical information at recruitment and at operation;
- Patient reported outcome data (prolapse symptoms, urinary, bowel and sexual function and EQ-5D) through questionnaires at 6, 12 and 24 months;
- Randomised women were examined 12 months after surgery to identify treatment success and adverse effects;
- Information about complications, readmissions, reoperations and costs.

Within the main PROSPECT trial short term failure (within two years of the prolapse operation) was captured. However, as prolapse is a progressive and relapsing condition, with surgery having a high failure rate¹ (repeat surgery occurs on average 12 years later) it is essential to capture the long term failure in order to truly evaluate the potential benefits of mesh versus its adverse effects, which may also occur many years later.² In addition, there is very little information about the long term effects of this condition on urinary, bowel and sexual function,

Current evidence

The Surgery for Prolapse Cochrane Review was updated in 2013.³ The review authors found 22 trials of mesh in prolapse surgery (3 used absorbable synthetic mesh; 7 used biological mesh; 12 used non-absorbable mesh). The data on biological mesh were at best conflicting, while women had both fewer symptoms and less objective prolapse after non-absorbable mesh at one year after surgery. However, few of the trials reported outcomes at two years or more, reporting of complications was sparse and none differentiated between primary and secondary repairs. Therefore, the overall benefits and costs of mesh in prolapse surgery remain undetermined. The Cochrane Review further identified the lack of long term follow-up data as a serious limitation.

The importance of long term follow-up has also been highlighted in the literature by the gynaecology community⁴ and NICE.⁵ Furthermore, lack of long term follow-up has been highlighted by NICE as a discussion point when counselling the patient for POP surgery. Long term follow-up of all of the PROSPECT participants is therefore necessary to inform health-care commissioners, health-care professionals and consumers alike. Such long term follow up will establish the (anticipated) benefits of mesh versus the likelihood of adverse effects such as mesh exposure, which may occur many years later.²

Methods

The PROSPECT participants will be contacted at 2-yearly intervals starting at 4 years after surgery and continuing to 14 years after surgery (6 questionnaires in total). For those women who were recruited into PROSPECT but who never received a prolapse operation as part of the trial, questionnaires will be issued at 2-yearly intervals starting at 4 years post-randomisation and continuing to 14 years post-randomisation. Woman who did not consent to be contacted in the future for long term follow-up or who had previously withdrawn from PROSPECT will be excluded from the long term follow-up study.

The questionnaire at each time-point will be identical and collect the same patient-reported outcome measures used in PROSPECT: prolapse symptoms; urinary, bowel and sexual function; EQ-5D; treatment failure including the need for additional surgery, pessaries, drugs or physiotherapy; postoperative complications including the need for additional surgical or conservative treatment; costs; and cost-effectiveness. In addition to postal questionnaire, HES (England) and ISD (Scotland) data will be requested to verify all preceding hospital re-admissions. Furthermore, case report verification will be carried out in the three lead centres (Aberdeen, Manchester and Plymouth) after the 6 year data collection is complete to verify and validate the other two data collection methods.

During the extended follow-up phase the same efficient retention system used in PROSPECT will be employed to ensure questionnaire return rates are maximised. This involves sending a reminder letter and further questionnaire three weeks after the original questionnaire is issued and not returned, followed by a postal or phone call reminder for continuing non-responders. The death notification service provided by the Health and Social Care Information Centre (HSCIC) will be utilised to minimise the risk of issuing a questionnaire to a participant who has subsequently died.

Loyalty and interest in the long term follow-up study will be maintained by continuing to send annual newsletters and Christmas cards to trial participants.

Primary outcome and power calculation

The primary clinical outcome measure for the main PROSPECT trial is the prolapse symptom score (POP-SS) at 12 months. In the long term follow-up study, the primary clinical outcome measure will be the POP-SS at 14 years. We estimate that if 400 patients in each arm of the primary trial respond to a questionnaire at 14 years (i.e. the current response rate is maintained over time), this will provide 96% power to detect a mean difference of 2 points (assuming SD=7 and alpha=0.025). If the response rate were to fall to 50% by 14 years, we would have 78% power to detect a difference of 2 POP-SS points.

Because of the importance of mesh in (theoretically) reducing the repeat surgery rate, we further propose that an additional primary clinical outcome will be the rate of repeat surgery for prolapse (any compartment). For repeat prolapse surgery within 14 years, if the event rate for the standard midline repair is assumed to be 25%, the power to detect a 10% absolute difference in reoperation rates compared with either biological or synthetic mesh would be 90% if the current response rate was maintained and 66% if the response rate falls to 50%.

The primary economic outcome measure of cost effectiveness will remain the same: the incremental cost per QALY (QALYs based on the EQ-5D⁶). In addition, because of all the potential problems associated with the use of mesh in prolapse surgery, serious adverse events will be included as a secondary outcome.

Following completion of the 14 year dataset, the full trial data will be reported for the randomised and the corresponding comprehensive cohort according to the trial

Statistical Analysis Plan. Analyses related to the two randomised trials (primary and secondary surgery) will be undertaken on an intention-to-treat basis allowing for repeated (two-yearly) symptom and quality of life measurements. Data from Cohort women will be analysed according to treatment received (mesh or no mesh surgery), separately according to primary or secondary procedure, or upper vaginal prolapse surgery only.

[figure not shown]
Management

Trial management, data collection and analysis will be undertaken in the PROSPECT Trial Office, HSRU, University of Aberdeen, under the supervised of the PROSPECT Project Management Group. This group consists of the grant holders and representatives from the Study Office.

References

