**Table 2: Number of participants randomised to each stratum in the primary RCT**

Stratum	Standard repair (A)	Synthetic mesh (B)	Biological mesh (C)
RCT1	253	256	255
RCT1B	178	181	n/a
RCT1C	116	n/a	114

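### The 14-year power in Protocol Appendix IV assumes more biological-mesh responders than women randomised to that arm, so power for standard versus biological mesh is overstated; the alpha rule for its two primary outcomes is also missing

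*Protocol*

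**What the plan says.** Protocol Appendix IV (Primary outcome and power calculation) starts from this input: "We estimate that if 400 patients in each arm of the primary trial respond to a questionnaire at 14 years". It explains the 400 as "i.e. the current response rate is maintained over time", without giving that rate. For POP-SS it states that "this will provide 96% power to detect a mean difference of 2 points (assuming SD=7 and alpha=0.025", and for lower response: "If the response rate were to fall to 50% by 14 years, we would have 78% power".

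The appendix then proposes that "an additional primary clinical outcome will be the rate of repeat surgery for prolapse (any compartment". With a 25% event rate after standard repair and a 10-point absolute difference from either mesh, its power "would be 90% if the current response rate was maintained and 66% if the response rate falls to 50"%. No alpha is restated for this outcome.

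Appendix IV gives 1353 women randomised in the primary trial and says that the 14-year data will be reported according to the trial SAP. SAP Table 2 ("Number of participants randomised to each stratum in the primary RCT") breaks the 1353 down by stratum. Under Primary/Secondary Outcomes, the SAP builds the biological comparison from RCT1 plus RCT1C (arms A and C only) and the synthetic comparison from RCT1 plus RCT1B (arms A and B only).

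Protocol section 2.7.2 explains alpha 0.025 as keeping an overall 0.05 with two tests, the two mesh comparisons. SAP General Methods gives a 5% significance level. Neither document says how alpha is shared between POP-SS and repeat surgery.

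**The concern.** The appendix was written after recruitment closed, with the final total in hand, yet it gives the biological arm more responders at 14 years than there were women randomised to it. Surgeons could randomise between two options when a mesh was unavailable, so the three arms are not equal thirds. A reader deciding whether the long-term phase can answer the biological-mesh question would take 96% and 90% at face value.

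The second matter is error control. An alpha that already allows for two comparisons is used again for a second primary outcome, which makes four primary tests at 0.025 in the primary trial.

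**Working it through.** **Inputs**

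- POP-SS: difference 2, SD 7, two-sided alpha 0.025 (Appendix IV), so z = 2.241.
- Repeat surgery: 25% v 15% (Appendix IV). Alpha 0.025 is inferred because it reproduces the stated power; alpha 0.05 would give 94.4% at 400 per arm, not 90%.
- Table 2, standard / synthetic / biological: RCT1 253 / 256 / 255; RCT1B 178 / 181 / –; RCT1C 116 / – / 114. The total is 764 + 359 + 230 = 1353, which agrees with Appendix IV.
- Biological comparison: 253 + 116 = 369 v 255 + 114 = 369.
- Synthetic comparison: 253 + 178 = 431 v 256 + 181 = 437.

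**Formulas** (unadjusted, normal approximation)

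- Means: power = Φ(2 / [7√(1/n₁ + 1/n₂)] − 2.241).
- Proportions: power = Φ([0.10 − 2.241·SE₀] / SE₁). With equal arms SE₀ = √(2 × 0.20 × 0.80 / n) = √(0.32/n) and SE₁ = √([0.25 × 0.75 + 0.15 × 0.85] / n) = √(0.315/n).

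**The plan's own figures**

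- n = 400 per arm. POP-SS: 4.041 − 2.241 = 1.799, giving 96.4%. Repeat surgery: (0.10 − 2.241 × 0.02828) / 0.02806 = 1.304, giving 90.4%.
- 50% response with equal thirds: 1353 / 3 / 2 = 225.5 per arm. POP-SS: 3.034 − 2.241 = 0.792, giving 78.6%. Repeat surgery: 0.417, giving 66.1%.

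All four stated figures reproduce, so the formula is sound and the fault is in the inputs. The 96% and 90% need only 400 per arm. The 78% and 66% need about 225 per arm, which is what an equal three-way split gives.

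**With the Table 2 counts**

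The current response rate is not stated. If 400 came from an equal third of 451, it is 400 / 451 = 88.7%; this is an inference, so a range is shown.

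| Standard v biological | n per arm | POP-SS | Repeat surgery |
|---|---|---|---|
| 100% response | 369 | 94.9% | 87.8% |
| 95% | 351 | 93.8% | 85.9% |
| 88.7% (inferred) | 327 | 92.1% | 83.3% |
| 80% | 295 | 89.1% | 78.9% |
| 50% | about 184 | 69.2% | 56.4% |

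For example, at n = 369 the POP-SS term is 3.881 − 2.241 = 1.640, giving 94.9%, and the repeat-surgery term is 1.164, giving 87.8%.

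Standard v synthetic (431 v 437): 95.7% and 89.2% at 88.7% response; 76.9% and 64.3% at 50%. These lie within about 2 points of the stated values.

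**Alpha over two outcomes**

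Two comparisons × two outcomes × 0.025 = 0.10, an upper bound on familywise error. If alpha were split to 0.0125 (an assumption that the documents do not make), biological power at 88.7% response would be 87.6% and 76.0%.

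**The case against.** Several counter-arguments have force.

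- **Adjustment.** The calculation above is unadjusted. The plan adjusts for baseline and, at 14 years, allows for repeated measurements, either of which could raise POP-SS power. At 327 per arm, a correlation of about 0.43 would restore 96%, since 1 − 327/400 = 0.18 ≈ 0.43². This stands as a possibility, but the documents give no correlation, and the appendix's own figure claims no such gain.
- **All controls.** Using all 547 standard-repair women would give about 96.0% and 89.4% at 88.7% response. The SAP does not plan this. Of its two planned biological analyses, 369 v 369 is the larger; RCT1 alone has 253 v 255.
- **Consequence.** Recruitment is closed, so no sample size changes, and at the inferred response biological power stays above 80%. That limits the weight of the point but does not make the figures right.

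A reader might also go further than the documents allow:

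- That all the stated power is too high. At 88.7% and 50% response, the synthetic comparison essentially matches the stated figures at alpha 0.025.
- That the appendix ignores its second primary outcome. It gives that outcome its own power at two response levels; what is missing is the alpha rule.
- That repeat surgery will rest on who returns a form at 14 years, with attrition bias to follow. Only the power scenario is tied to response. The appendix plans six questionnaires and says that "HES (England) and ISD (Scotland) data will be requested to verify all preceding hospital re-admissions"; Protocol section 5.2 already uses central data to supplement and validate women's reports, and section 6.3 names Cox regression for time to further surgery.

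**Conclusion.** The point holds for standard versus biological mesh. Four hundred biological responders cannot come from 369 women, and the stated 96% and 90% exceed what the appendix's own method gives at any response rate. At the inferred 88.7% response the overstatement is about 4 points for POP-SS (92% against 96%) and 7 for repeat surgery (83% against 90%). At 50% response it is about 9 and 10 points (69% against 78%, 56% against 66%). These sizes rest on the SAP's combined-stratum sets, two-sided alpha 0.025 and no covariate adjustment. That the 96% and 90% cannot be reached does not depend on the inferred response rate.

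The missing alpha rule is a separate, real gap. The 10% is a bound, not an estimate of the actual error rate, and nothing in the documents requires a split; a fixed sequence would leave alpha for the first outcome unchanged.

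**What to change.** 1. In Appendix IV, replace the single per-arm calculation with one for each comparison from Table 2 (369 v 369 and 431 v 437), and show a range of response rates with the current rate stated. If a gain from adjustment or repeated measures is to be claimed, give the assumed correlation.
2. State how alpha is controlled over POP-SS and repeat surgery, for example by a fixed sequence or a split, and give power at the resulting levels.
3. Optionally, use the HES and ISD data already requested as a main source for repeat surgery, not only for verification, in all women with record-access consent. Full ascertainment of everyone randomised would give at most 88% (biological) and 93% (synthetic) at alpha 0.025. Women who withdrew or did not consent lower that ceiling, and privately paid operations would still need the questionnaire.

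The first two are wording changes to the appendix and SAP; the third uses data already planned. The cost is a less favourable stated power for biological mesh and, if alpha is split, for both comparisons.
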